#### 4. Study Design Diagrams

[figure not shown]
[figure not shown]

Figure- Alternate analysis approaches

[figure not shown]
- ■ ■ ■ Included person-time
- ■ ■ ■ Excluded person-time

Provides 'on treatment' estimates for the outcome risk and addresses exposure person-time misclassification

### Analysis 1

[figure not shown]

### Analysis 3

[figure not shown]
Addresses misclassification of outcome onset

### Analysis 2

Addresses reverse causation due to preferential treatment initiation related to unrecorded cognitive impairment at study start and informative-censoring

### Analysis 4

Addresses outcome misclassification

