#### *Inclusion criteria for analysis 2:*

- Aged  $\geq 65$  years on the index date
- 365 days enrollment in Medicare Parts A, B, and D with no HMO coverage prior to index date
- No use of Anastrozole vs Exemestane or Letrozole, any time prior to index date (all available lookback approach with a minimum of 365 days)
- No diagnosis of dementia any time prior to and including index date
- No history of nursing home admission recorded in any time prior to and including index date
- At least two claims with breast cancer diagnosis recorded in 365 days prior to index date (ICD-9 174.x, 175.x, 233.0, V10.3 or ICD-10 C50.x19, C05.90, Z85.3)

- 180-day continuous use of Anastrozole vs Exemestane or Letrozole starting on the index date

c. Flowchart of the study cohort assembly

	Less Excluded Patients	Remaining Patients
All patients		23,466,175
Did not meet cohort entry criteria	-23,372,404	93,771
Excluded due to insufficient enrollment	-59,468	34,303
Excluded based on Dementia Exclusion	-4,796	29,507
Excluded based on Nursing Home Admission	-5,115	24,392
Excluded based on Breast Cancer Diagnosis	-5,939	18,453
Excluded anyone aged <65 at index	-1,464	16,989
Patients in Anastrozole group		10,926
Patients in Exemestane or Letrozole group		6,063
Final cohort		16,989

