Targeted therapy Antibody drug conjugates (Ado-trastuzumab emtansine, Fam-trastuzumab deruxtecan, Sacituzumab govitecan, Sacituzumab govitecan) Monoclonal antibodies (Trastuzumab, Pertuzumab, hyaluronidase, Margetuximab) Kinase inhibitors (Lapatinib, Neratinib, Tucatinib) CDK4/6 inhibitors (Palbociclib, ribociclib, abemaciclib) mTOR inhibitor (Everolimus) PI3K inhibitor (Alpelisib) PARP inhibitors (Olaparib, talazoparib)	Immunotherapy PD-1 inhibitor (Pembrolizumab)
Radiation therapy, beam therapy or brachytherapy	Breast surgery Lumpectomy Mastectomy

ICD-9, ICD-10, HCPCS, and NDC codes used to define the covariates listed above are available in Appendix A.

c. Outcome variables and study follow-up:

- **Primary outcome:** incident dementia, i.e., Alzheimer's disease, vascular dementia, senile, presenile, or unspecified dementia, or dementia in other diseases classified elsewhere. Outcome will be defined by 1 inpatient claim or 2 outpatient claims in analysis 1, 2, 3. In analysis 4, the outcome will be defined by 1 inpatient or 1 outpatient claims and 1 prescription claim for a symptomatic treatment [donepezil, galantamine, rivastigmine, and memantine] within 6 months of each other with outcome date assigned to second event in the sequence.
- Secondary outcomes: Individual component:  
Alzheimer's disease

Condition	ICD-9 and ICD-10 codes
Alzheimer's disease	331.0*, F00*, G30*
Vascular dementia	290.4*, F01*
Senile, presenile, or unspecified dementia	290.0*, 290.1*, 290.3*, 797*, F03*
Dementia in other diseases classified elsewhere	331.1*, 331.2*, 331.7*, 294.1*, F02*

For analysis 1,3, and 4 the follow-up will start the day after initiation of Anastrozole and Exemestane or Letrozole and will continue until the earliest date of the following events:

- The first occurrence of the outcome of interest
- The date of end of continuous registration in the database,
- End of the study period,
- Measured death event occurs,
- The date of drug discontinuation, defined as the date of the last continuous treatment episode of the index drug (Anastrozole and Exemestane or Letrozole) plus a defined grace period (i.e., 90 days after the end of the last prescription's days' supply in main analyses).

For analysis 2, the follow-up will start 180 days after initiation of Anastrozole and Exemestane or Letrozole and will continue until the earliest date of the following events:

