- The first occurrence of the outcome of interest, unless otherwise specified for selected outcomes,
- The date of end of continuous registration in the database,
- End of the study period,
- Measured death event occurs,

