**DREAM study protocol - Comparison 11 Anastrozole vs Exemestane or Letrozole**

- Maximum allowed follow-up time (1095 days) reached

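### Analysis 2 guards against informative discontinuation only after day 180; before that its continuous-use entry rule replaces informative censoring with selection on a post-index event

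*Combined protocol and SAP*

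**What the plan says.** Section 4 (Study Design Diagrams) gives the purpose of Analysis 2: "Addresses reverse causation due to preferential treatment initiation related to unrecorded cognitive impairment at study start and informative-censoring".

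Section 6c sets two follow-up schemes.

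- **Analyses 1, 3 and 4:** "For analysis 1,3, and 4 the follow-up will start the day after initiation of Anastrozole and Exemestane or Letrozole". The end events include "The date of drug discontinuation, defined as the date of the last continuous treatment episode of the index drug" plus a grace period, given as "90 days after the end of the last prescription's days' supply in main analyses".
- **Analysis 2:** "For analysis 2, the follow-up will start 180 days after initiation of Anastrozole and Exemestane or Letrozole". Its list opens with "The first occurrence of the outcome of interest, unless otherwise specified for selected outcomes", continues with end of registration, end of study and death, and closes with "Maximum allowed follow-up time (1095 days) reached". Drug discontinuation is not on it.

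Section 5b adds one entry criterion for Analysis 2 only: "180-day continuous use of Anastrozole vs Exemestane or Letrozole starting on the index date". The plan does not say whether the 90-day grace period counts toward those 180 days. The flowchart in section 5c has no row for this criterion, and the balance table in section 8 shows no separate Analysis 2 cohort.

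**The concern.** Analysis 2 is the only analysis that keeps following patients after they stop treatment, so the informative-censoring claim rests on it. Its entry rule is itself decided by stopping, over the 180 days after the index date. For early stoppers, informative censoring becomes selection on the same event.

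Nothing else in the plan repairs this. The propensity score in section 7 models initiation from baseline covariates. It does not balance 180-day persisters if persistence depends on unmeasured cognition or frailty, and section 4 itself raises unrecorded cognitive impairment. Section 9 treats death as a competing event but plans no censoring weights or other adjustment for discontinuation.

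What is at stake is interpretation. If Analysis 2 agrees with Analyses 1, 3 and 4, a reader will naturally conclude that informative censoring does not matter. That conclusion would not follow for stopping in the first 180 days.

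**Working it through.** **1. The plan's own figures.** The section 5c flowchart reproduces: 23,466,175 − 23,372,404 = 93,771; − 59,468 = 34,303; − 4,796 = 29,507; − 5,115 = 24,392; − 5,939 = 18,453; − 1,464 = 16,989 = 10,926 + 6,063. No step removes patients for lack of 180-day use. The matched set in section 8 is 2 × 5,508 = 11,016.

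**2. The rules applied to a patient whose supply ends on day t.** Analyses 1, 3 and 4 follow to day t + 90, absent an earlier end event. Analysis 2 entry needs t ≥ 180 (strict reading), or t + 90 ≥ 180 if grace counts as use.

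| t | Analyses 1, 3, 4 end | Analysis 2, strict | Analysis 2, grace counts |
|---|---|---|---|
| 60 | day 150 | excluded | excluded |
| 90 | day 180 | excluded | enters |
| 179 | day 269 | excluded | enters |
| 365 | day 455 | enters, not censored at stopping | same |

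For t = 60, dementia recorded after day 150 is counted in no planned analysis. The affected group is all t < 180 on the strict reading and t < 90 if grace counts.

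**3. How many.** The documents give no stopping rate. If 10% to 30% stopped before day 180 (assumption), 11,016 × 0.10 = 1,102 to 11,016 × 0.30 = 3,305 matched patients would be affected on the strict reading. Section 8 does not say that this matched set feeds Analysis 2.

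**4. Possible size, with no drug effect.** All inputs here are assumptions. A share q of initiators is prodromal with k times the dementia hazard. Non-prodromal patients stop by day 180 at 20% in both arms; prodromal patients stop at rate p, which may differ by arm.

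- Prodromal share among persisters: s = q(1 − p) / [q(1 − p) + (1 − q) × 0.8].
- Mean relative hazard at day 180: 1 + (k − 1)s.

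For q = 0.10 and k = 5:

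- p = 0.50: s = 0.05/0.77 = 0.0649; hazard 1.260.
- p = 0.25: s = 0.075/0.795 = 0.0943; hazard 1.377.
- Ratio: 1.260/1.377 = 0.915.

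Over q = 0.05 to 0.20, k = 3 to 5, and p = 0.40 to 0.50 versus 0.25, the ratio runs from 0.876 (q = 0.20, k = 5, p = 0.50) to 0.983 (q = 0.05, k = 3, p = 0.40). With equal p in both arms it is exactly 1.0.

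**5. Direction, by simulation with a true ratio of 1.0.** Assumptions: half the patients frail; dementia 4% per year if frail, 1% otherwise; stopping 0.25 per year, raised to 1.5 per year in frail patients of one arm. Deaths are ignored, and follow-up in every analysis is cut at 1095 days from index. Rate ratios:

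| Differential stopping | Analysis 1 | Analysis 2, strict | Analysis 2, grace counts | All initiators from day 180 |
|---|---|---|---|---|
| After day 180 only | 0.84 | 1.00 | 1.00 | 1.00 |
| Before day 180 only | 0.86 | 0.82 | 0.90 | 0.99 to 1.00 |
| Both | 0.75 | 0.82 | 0.90 | 1.00 |

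Analysis 2 removes the late bias. In the early-only case Analyses 1 and 2 err in the same direction, so their agreement would reassure falsely.

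**The case against.** Several stronger readings are tempting, and the documents do not support them.

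- A reader might infer that early stoppers are followed nowhere. Section 6c contradicts this: Analyses 1, 3 and 4 count their person-time and events to 90 days after supply ends, up to day 269 for a stop on day 179. The gap is follow-up beyond that point.
- A reader might infer that Analysis 2 fails altogether at its informative-censoring aim. It does not: it does not censor at discontinuation, so stopping after day 180 is handled. Section 4 says that it addresses the problem, not that it eliminates it. In the simulation with both early and late differential stopping it is nearer the truth than Analysis 1.
- A reader might infer that every patient stopping before day 180 is certainly excluded. That depends on an undefined term. If grace counts, stoppers at days 90 to 179 enter and are followed.
- A reader might take 0.88 to 0.98 as an estimate of bias in this study. It is not. The documents give no stopping rates and no evidence that the arms differ in stopping, and the comparison is between initiators of active drugs.

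There is also a case for the persistence rule: it limits exposure misclassification in follow-up that ignores later stopping. That justifies keeping Analysis 2, but not relying on it for early discontinuation. The design figures are not available here, so this reading rests on the text.

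**Conclusion.** The concern holds in a limited form. Analysis 2 protects against informative discontinuation after day 180 and not before it. No planned analysis follows early stoppers beyond 90 days after supply ends; that group is everyone stopping before day 180 on the strict reading, or before about day 90 if grace counts. Matching initiators on baseline covariates does not remove the resulting selection.

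Bias arises only if early stopping is related to unrecorded cognition or frailty differently by arm. Its size cannot be derived from the documents; the figures above show direction and plausible scale under stated assumptions only. This is a worthwhile, inexpensive improvement rather than a flaw that invalidates the plan.

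**What to change.** - Add Analysis 2b: the Analysis 2 day-180 start, 1095-day cap and censoring list, without the continuous-use criterion. Enter all matched initiators who are alive, enrolled and free of recorded dementia at day 180, analysed by index drug. The dementia-free condition must be explicit, because the section 5b exclusion reaches only to the index date.
- Keep the present Analysis 2 as the persistent-user analysis. State whether the grace period counts toward its 180 days, and report the number excluded by this criterion in each arm.
- In section 4, limit the informative-censoring claim for Analysis 2 to discontinuation after day 180, and rely on 2b for earlier discontinuation.

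The cost is one more run on data already held, a count by arm, and a sentence each in sections 4, 5b and 6c. The downside is that 2b includes off-drug time, so its estimate is diluted towards the null. It should therefore be read beside Analysis 2 and not replace it.

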## 6. Variables

### a. Exposure-related variables:

#### Study drug:

The study exposure of interest is initiation of Anastrozole

#### Comparator:

Exemestane or Letrozole

### b. Covariates:

Demographics	
Age	Region
Gender	Calendar year of index date
Race	Low income subsidy

Dementia risk factors	
Diabetes	Depression
Obesity	Anxiety
Hypertension	Bipolar disorder
Coronary artery disease	Schizophrenia

Markers for healthy behavior, frailty, healthcare use	
Smoking	Number of hospitalizations
Mammography	Number of physician office visits
Colonoscopy	Number of serum creatinine tests ordered
Fecal occult blood test	Composite frailty score
Influenza vaccination	Number of C-reactive protein tests ordered
Pneumococcal vaccination	Osteoporosis
Herpes zoster vaccination	Fractures

Bone mineral density test	Falls
Number of distinct generic agents	Use of supplemental oxygen
Number of emergency room visits	Combined comorbidity score
Number of outpatient visits	Alcohol abuse

Comedication use	
Lithium	Diuretics
Anti-epileptic mood stabilizers	Nitrates
Anti-epileptics (other than mood stabilizers)	Lipid lowering drugs
Atypical antipsychotics	Non-insulin diabetes medications
Benzodiazepines	Insulin
Serotonin-norepinephrine reuptake Inhibitors	Antidepressants
Selective serotonin reuptake inhibitors	Angiotensin II receptor blockers (ARBs)
Tricyclic antidepressants (TCAs)	Angiotensin converting enzyme inhibitors (ACEi)
Typical antipsychotics	Calcium channel blockers
Anticoagulants	Beta blockers
Antiplatelet agents	

Comorbid conditions	
Atrial fibrillation	Chronic liver disease
Coronary artery disease	Asthma
Heart failure	Ischemic heart disease
Stroke or transient ischemic attack	Chronic obstructive pulmonary disease
Peripheral vascular disease	Malignancy
Hyperlipidemia	Drug or alcohol abuse or dependence
Renal dysfunction	Venous thromboembolism
Rheumatoid Arthritis	Hypertension

Other Breast Cancer treatments and Breast Cancer severity indicators	
Chemotherapy	Hormone therapy agents

Anthracyclines (Doxorubicin, Epirubicin) Taxanes (Paclitaxel, docetaxel) 5-fluorouracil Capecitabine Cyclophosphamide Carboplatin Ixabepilone Eribulin Platinum agents (Cisplatin, carboplatin) Vinorelbine Capecitabine Gemcitabine	Tamoxifen Toremifene Fulvestrant Goserelin Leuprolide Estradiol Megestrol acetate Androgens, testosterone
Targeted therapy Antibody drug conjugates (Ado-trastuzumab emtansine, Fam-trastuzumab deruxtecan, Sacituzumab govitecan, Sacituzumab govitecan) Monoclonal antibodies (Trastuzumab, Pertuzumab, hyaluronidase, Margetuximab) Kinase inhibitors (Lapatinib, Neratinib, Tucatinib) CDK4/6 inhibitors (Palbociclib, ribociclib, abemaciclib) mTOR inhibitor (Everolimus) PI3K inhibitor (Alpelisib) PARP inhibitors (Olaparib, talazoparib)	Immunotherapy PD-1 inhibitor (Pembrolizumab)
Radiation therapy, beam therapy or brachytherapy	Breast surgery Lumpectomy Mastectomy

ICD-9, ICD-10, HCPCS, and NDC codes used to define the covariates listed above are available in Appendix A.

c. Outcome variables and study follow-up:

- **Primary outcome:** incident dementia, i.e., Alzheimer's disease, vascular dementia, senile, presenile, or unspecified dementia, or dementia in other diseases classified elsewhere. Outcome will be defined by 1 inpatient claim or 2 outpatient claims in analysis 1, 2, 3. In analysis 4, the outcome will be defined by 1 inpatient or 1 outpatient claims and 1 prescription claim for a symptomatic treatment [donepezil, galantamine, rivastigmine, and memantine] within 6 months of each other with outcome date assigned to second event in the sequence.
- Secondary outcomes: Individual component:  
Alzheimer's disease

Condition	ICD-9 and ICD-10 codes
Alzheimer's disease	331.0*, F00*, G30*
Vascular dementia	290.4*, F01*
Senile, presenile, or unspecified dementia	290.0*, 290.1*, 290.3*, 797*, F03*
Dementia in other diseases classified elsewhere	331.1*, 331.2*, 331.7*, 294.1*, F02*

For analysis 1,3, and 4 the follow-up will start the day after initiation of Anastrozole and Exemestane or Letrozole and will continue until the earliest date of the following events:

- The first occurrence of the outcome of interest
- The date of end of continuous registration in the database,
- End of the study period,
- Measured death event occurs,
- The date of drug discontinuation, defined as the date of the last continuous treatment episode of the index drug (Anastrozole and Exemestane or Letrozole) plus a defined grace period (i.e., 90 days after the end of the last prescription's days' supply in main analyses).

For analysis 2, the follow-up will start 180 days after initiation of Anastrozole and Exemestane or Letrozole and will continue until the earliest date of the following events:

- The first occurrence of the outcome of interest, unless otherwise specified for selected outcomes,
- The date of end of continuous registration in the database,
- End of the study period,
- Measured death event occurs,

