## 7. Propensity score analysis

We will use a propensity-score (PS)-based approach to account for measured confounding in this study. The PS will be calculated as the predicted probability of initiating the exposure of interest (i.e., the repurposing candidate) versus the reference drug conditional on baseline covariates using multivariable logistic regression constructed separately in each data source. On average, patients with similar PSs have similar distribution of potential confounders used to estimate the PS. Therefore, analyses conditioned on the PS provide effect estimates that are free from measured confounding. For all our analyses, initiators of each exposure of interest will be matched with initiators of the reference exposure based on their PS within each data source. Pair matching will be conducted using a nearest-neighbor algorithm, which seeks to minimize the distance between propensity scores in each pair of treated and reference patients, and a caliper of 0.025 on the natural scale of the PS will be used to ensure similarity between the matched patients.

We report multiple diagnostics for PS analysis in this protocol. First, the PS distributional overlap is provided between two groups before and after matching to ensure comparability of these groups. Next, balance in each individual covariate between two treatment groups is reported using standardized differences.

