## 8. Table for covariate balance

	Crude			PS-Matched		
Variable	Anastrozole (N = 10,926)	Exemestane or Letrozole (N = 6,063)	St. Diff	Anastrozole (N = 5,508)	Exemestane or Letrozole (N = 5,508)	St. Diff
Demographics						
Age, mean (SD)	73.7 (6.1)	73.8 (6.3)	-0.02	73.9 (6.4)	73.9 (6.3)	0.01
Gender, n (%)						
Male	41 (0.4)	40 (0.7)	-0.04	29 (0.5)	28 (0.5)	0.00
Female	10885 (99.6)	6023 (99.3)	0.04	5479 (99.5)	5480 (99.5)	0.00
Race, n (%)						
White	9669 (88.5)	5351 (88.3)	0.01	4820 (87.5)	4855 (88.1)	-0.02
Black	744 (6.8)	407 (6.7)	0.00	400 (7.3)	379 (6.9)	0.02
Hispanic	96 (0.9)	56 (0.9)	-0.01	60 (1.1)	51 (0.9)	0.02
Other	417 (3.8)	249 (4.1)	-0.02	228 (4.1)	223 (4)	0.01
Region, n (%)						
Northeast; n (%)	2188 (20)	1168 (19.3)	0.02	1086 (19.7)	1080 (19.6)	0.00
South; n (%)	3912 (35.8)	2431 (40.1)	-0.09	2174 (39.5)	2156 (39.1)	0.01
Midwest; n (%)	2877 (26.3)	1266 (20.9)	0.13	1207 (21.9)	1210 (22)	0.00
West; n (%)	1936 (17.7)	1189 (19.6)	-0.05	1035 (18.8)	1053 (19.1)	-0.01
Other; n (%)	13 (0.1)	9 (0.1)	-0.01	6 (0.1)	9 (0.2)	-0.02
Calendar year of index date, n (%)						
2014	2409 (22)	1313 (21.7)	0.01	1160 (21.1)	1222 (22.2)	-0.03
2015	2470 (22.6)	1326 (21.9)	0.02	1217 (22.1)	1211 (22)	0.00
2016	2154 (19.7)	1210 (20)	-0.01	1135 (20.6)	1102 (20)	0.02

DREAM study protocol - Comparison 11 Anastrozole vs Exemestane or Letrozole

2017	1950 (17.8)	1110 (18.3)	-0.01	1001 (18.2)	992 (18)	0.00
2018	1943 (17.8)	1104 (18.2)	-0.01	995 (18.1)	981 (17.8)	0.01
Low income subsidy, n (%)	1197 (11)	645 (10.6)	0.01	632 (11.5)	582 (10.6)	0.03
Dementia risk factors, n (%)						
Anxiety	2220 (20.3)	1238 (20.4)	0.00	1142 (20.7)	1125 (20.4)	0.01
Bipolar disorder	109 (1)	71 (1.2)	-0.02	63 (1.1)	61 (1.1)	0.00
Coronary artery disease	1985 (18.2)	1111 (18.3)	0.00	1011 (18.4)	1008 (18.3)	0.00
Depression	1887 (17.3)	1083 (17.9)	-0.02	991 (18)	978 (17.8)	0.01
Diabetes	3114 (28.5)	1788 (29.5)	-0.02	1599 (29)	1621 (29.4)	-0.01
Hypertension	8496 (77.8)	4606 (76)	0.04	4236 (76.9)	4228 (76.8)	0.00
Obesity	2518 (23)	1306 (21.5)	0.04	1249 (22.7)	1223 (22.2)	0.01
Schizophrenia	19 (0.2)	9 (0.1)	0.01	12 (0.2)	9 (0.2)	0.01
Markers for healthy behavior, frailty, healthcare use						
Bone mineral density test, n (%)	4106 (37.6)	1926 (31.8)	0.12	1876 (34.1)	1855 (33.7)	0.01
Colonoscopy, n (%)	1030 (9.4)	601 (9.9)	-0.02	551 (10)	543 (9.9)	0.01
Fecal occult blood test, n (%)	1033 (9.5)	563 (9.3)	0.01	538 (9.8)	524 (9.5)	0.01

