Herpes zoster vaccination, n (%)	6 (0.1)	2 (0)	0.01	2 (0)	2 (0)	0.00
Influenza vaccination, n (%)	7203 (65.9)	3926 (64.8)	0.03	3613 (65.6)	3589 (65.2)	0.01
Mammography, n (%)	6944 (63.6)	3291 (54.3)	0.19	3159 (57.4)	3163 (57.4)	0.00
Pneumococcal vaccination, n (%)	4881 (44.7)	2651 (43.7)	0.02	2464 (44.7)	2427 (44.1)	0.01
Smoking, n (%)	3320 (30.4)	1820 (30)	0.01	1713 (31.1)	1666 (30.2)	0.02
Number of C-reactive protein tests ordered, mean (SD)	0.1 (0.6)	0.1 (0.6)	-0.01	0.1 (0.6)	0.1 (0.6)	0.00

DREAM study protocol - Comparison 11 Anastrozole vs Exemestane or Letrozole

Number of emergency room visits, mean (SD)	0.5 (0.9)	0.5 (1)	-0.05	0.5 (0.9)	0.5 (1)	-0.02
Number of distinct prescriptions, mean (SD)	10.9 (5.5)	11 (5.7)	-0.01	10.9 (5.6)	11 (5.7)	-0.01
Number of hospitalizations, mean (SD)	0.2 (0.5)	0.2 (0.5)	-0.03	0.2 (0.5)	0.2 (0.5)	-0.01
Number of outpatient visits, mean (SD)	14.4 (8.2)	14.9 (8.7)	-0.06	14.5 (8.5)	14.7 (8.5)	-0.02
Number of physician office visits, mean (SD)	14.4 (8.2)	14.9 (8.7)	-0.06	14.5 (8.5)	14.7 (8.5)	-0.02
Number of serum creatinine tests ordered, mean (SD)	1.4 (2.1)	1.4 (2)	0.01	1.4 (2)	1.4 (1.9)	0.01
Composite frailty score, mean (SD)	0.2 (0)	0.2 (0)	-0.06	0.2 (0)	0.2 (0)	-0.01
Falls, n (%)	525 (4.8)	299 (4.9)	-0.01	265 (4.8)	272 (4.9)	-0.01
Fractures, n (%)	723 (6.6)	481 (7.9)	-0.05	384 (7)	395 (7.2)	-0.01
Osteoporosis, n (%)	2535 (23.2)	1371 (22.6)	0.01	1256 (22.8)	1261 (22.9)	0.00
Use of supplemental oxygen, n (%)	138 (1.3)	55 (0.9)	0.03	49 (0.9)	54 (1)	-0.01
Combined comorbidity score, mean (SD)	3.4 (3.1)	4.1 (3.3)	-0.24	3.8 (3.2)	3.8 (3.2)	0.01
Comedication use, n (%)						
Angiotensin converting enzyme inhibitors (ACEi)	2867 (26.2)	1519 (25.1)	0.03	1395 (25.3)	1398 (25.4)	0.00
Angiotensin II receptor blockers (ARBs)	2716 (24.9)	1474 (24.3)	0.01	1369 (24.9)	1360 (24.7)	0.00
Antidepressants	3036 (27.8)	1726 (28.5)	-0.02	1521 (27.6)	1550 (28.1)	-0.01
Beta blockers	3625 (33.2)	2040 (33.6)	-0.01	1867 (33.9)	1855 (33.7)	0.01

DREAM study protocol - Comparison 11 Anastrozole vs Exemestane or Letrozole

Calcium channel blockers	2513 (23)	1357 (22.4)	0.02	1250 (22.7)	1259 (22.9)	0.00
DMARD	334 (3.1)	170 (2.8)	0.02	157 (2.9)	160 (2.9)	0.00
Diuretics	4685 (42.9)	2467 (40.7)	0.04	2286 (41.5)	2292 (41.6)	0.00
Insulin	583 (5.3)	325 (5.4)	0.00	291 (5.3)	301 (5.5)	-0.01
Lipid lowering drugs	5814 (53.2)	3070 (50.6)	0.05	2843 (51.6)	2846 (51.7)	0.00
Nitrates	391 (3.6)	222 (3.7)	0.00	193 (3.5)	203 (3.7)	-0.01

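### The propensity score lists no separate metastatic or stage indicator, so balance on advanced cancer is neither targeted nor shown, although the listed treatment proxies do balance after matching

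*Combined protocol and SAP*

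**What the plan says.** Section 7 estimates the propensity score "conditional on baseline covariates using multivariable logistic regression" and matches pairs on it. It claims freedom from measured confounding only.

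The covariates for cancer severity are in Section 6b under "Other Breast Cancer treatments and Breast Cancer severity indicators". The items are chemotherapy, hormone, targeted and immunotherapy agents, breast surgery, and "Radiation therapy, beam therapy or brachytherapy". All are treatments. The only other cancer item in Section 6b is 'Malignancy', under comorbid conditions. For definitions the section says that "HCPCS, and NDC codes used to define the covariates listed above are available in Appendix A"; that appendix is not part of the text available for this review.

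Section 8 reports balance for six breast cancer rows (surgery, chemotherapy, hormone agents, immunotherapy, radiation, targeted therapy), for 'Malignancy' and for a combined comorbidity score whose components are not given. It has no row for stage, nodal status or secondary malignancy.

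**The concern.** Extent of disease can plausibly influence which aromatase inhibitor is started, how long the patient lives and stays on it, and how much contact with care there is in which dementia could be recorded. Under Section 6c all analyses end follow-up at death, and analyses 1, 3 and 4 also end it at discontinuation. Section 9 fits a cause-specific hazard model and notes that competing death matters if mortality differs between groups. An imbalance in metastatic disease could therefore bear on the dementia comparison.

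The matched table shows that the arms received similar classes of treatment. It does not show directly that they had similar disease. A treatment class may be absent because disease was advanced, or because treatment was given before the baseline window. A treated/untreated row cannot tell these apart.

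**Working it through.** **Inputs.** All counts are from Section 8: crude N = 10,926 (anastrozole) and 6,063 (exemestane or letrozole); matched N = 5,508 per arm.

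**Step 1: reproduce the plan's figures.** For proportions, d = (p1 - p2) / sqrt{[p1(1 - p1) + p2(1 - p2)] / 2}.

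| Row | Crude counts | Crude % | d recomputed | d printed | Matched counts | d printed, matched |
|---|---|---|---|---|---|---|
| Breast surgery | 9099 vs 3988 | 83.3 vs 65.8 | 0.410 | 0.41 | 3980 vs 3977 | 0.00 |
| Targeted therapy | 34 vs 232 | 0.3 vs 3.8 | -0.249 | -0.25 | 34 vs 34 | 0.00 |
| Radiation | 5121 vs 2299 | 46.9 vs 37.9 | 0.182 | 0.18 | 2228 vs 2236 | 0.00 |
| Hormone agents | 1088 vs 865 | 10.0 vs 14.3 | -0.132 | -0.13 | 682 vs 682 | 0.00 |
| Chemotherapy | 2120 vs 1460 | 19.4 vs 24.1 | -0.114 | -0.11 | 1203 vs 1205 | 0.00 |
| Immunotherapy | 1 vs 1 | 0 vs 0 | -0.006 | -0.01 | 1 vs 1 | 0.00 |
| Malignancy | 10906 vs 6054 | 99.8 vs 99.9 | -0.009 | -0.01 | 5500 vs 5499 | 0.01 |

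For the comorbidity score, (3.4 - 4.1) / sqrt[(3.1² + 3.3²) / 2] = -0.22. Rounding of the printed means allows -0.19 to -0.25, which is consistent with the printed -0.24. The matched value is 0.01. All printed figures are reproduced.

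**Step 2: what the rows can tell us.** Malignancy is absent in 20 + 9 = 29 of 16,989 patients (0.17%), as expected when entry requires two breast cancer claims. It cannot separate early from advanced disease. Immunotherapy, at one patient per arm, is also uninformative. The other five treatment rows and the comorbidity score are imbalanced before matching. The crude gap in the score is not mirrored in the rows listed as comorbid conditions, where the largest crude difference is 0.08 in absolute value (chronic liver disease). The documents do not say what drives it.

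**Step 3: what matching does.** It leaves out 6,063 - 5,508 = 555 comparator patients (9.2%). Comparator users of targeted therapy fall from 232 to 34, so 198 (85%) are among those left out. In the matched sample 5,508 - 3,980 = 1,528 and 5,508 - 3,977 = 1,531 patients (about 28% of each arm) have no recorded breast surgery. These groups are equal in size, but their mix of advanced disease and earlier surgery is not shown.

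**Step 4: illustrative size.** The documents give neither the prevalence of metastatic disease after matching nor its association with recorded dementia. Both are assumed here. With residual prevalence p1 (anastrozole) and p0 (comparator) and hazard ratio R of metastatic disease for recorded dementia, the approximate factor on the treatment hazard ratio is [1 + p1(R - 1)] / [1 + p0(R - 1)].

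| Assumed p1 vs p0 | R = 0.5 | R = 1.5 | R = 2 | R = 3 |
|---|---|---|---|---|
| 5% vs 10% | 0.975/0.95 = 1.03 | 1.025/1.05 = 0.98 | 1.05/1.10 = 0.95 | 1.10/1.20 = 0.92 |
| 8% vs 15% | 0.96/0.925 = 1.04 | 1.04/1.075 = 0.97 | 1.08/1.15 = 0.94 | 1.16/1.30 = 0.89 |

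The factor crosses 1 as R does, so even the direction is open.

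**The case against.** The strongest reply is that the analysis is run in the matched sample, where all six treatment rows stand at 0.00 and the comorbidity score at 0.01. Most comparator users of targeted therapy are no longer in it. The comorbidity score may already count metastatic disease, and the code lists in Appendix A could settle that. All of this stands. It lowers the likely residual imbalance, but it does not measure it.

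Several stronger readings are tempting and are not supported:

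- *The crude table proves that comparator patients have later-stage cancer.* No stage is reported. Section 5b admits history codes (V10.3, Z85.3) and the baseline period is 365 days. Less recent surgery, radiation and mammography with more prior hormone therapy also fits longer time since diagnosis. General illness markers are close before matching (hospitalizations -0.03, frailty score -0.06), and supplemental oxygen is more frequent in the anastrozole arm (1.3% vs 0.9%).
- *The matched hormone row, 682 vs 682, hides different disease because it pools several agents.* This is possible, but no counts by agent are given.
- *The matched hazard ratio is biased.* The prevalences and hazard ratios in Step 4 are assumptions, and the range spans both directions.
- *A planned visit covariate was never extracted.* The row "Number of physician office visits, mean (SD") prints the same values as the outpatient visit row in every column: 14.4 (8.2), 14.9 (8.7), -0.06, then 14.5 (8.5), 14.7 (8.5), -0.02. These are rounded values, and the two items may share a definition in Appendix A. If they are duplicates, one is redundant and does not bias the score.

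**Conclusion.** The point holds as a gap in the covariate set and in the evidence of comparability. No metastatic or stage indicator is separately listed in Section 6b or shown in Section 8, the one general cancer diagnosis is near-constant, and the crude proxies show that the arms differ in cancer treatment history. Matching on those proxies is reassuring but indirect. The conclusion assumes that Appendix A does not define such an indicator under another name; partial capture through the comorbidity score cannot be excluded.

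The size and direction of residual bias are unknown. The factor of about 0.89 to 1.04 is an illustration that rests wholly on the assumed values. This is a cheap improvement the plan should make, not evidence that the matched comparison is wrong.

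**What to change.** Add a baseline indicator of secondary malignancy from claims (ICD-9 196-198, ICD-10 C77-C79) to Section 6b, to the propensity score model and to the Section 8 table, then refit and rematch. State in the plan whether the combined comorbidity score includes metastatic disease. If the indicator proves balanced, the plan gains the direct evidence it now lacks.

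The cost is one code-defined covariate from claims already in hand, one rerun of the propensity score and possibly a few lost matches. It is best done before outcomes are compared; the document shows no outcome results.

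Minor: check why the outpatient and physician office visit rows print identical values, and correct or drop one. Removing 'Malignancy' would change almost nothing and is optional.
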